In CM-012, a multi-cohort phase Ib trial evaluating the safety and tolerability of nivolumab in chemotherapy-naive NSCLC either as monotherapy or in combination with other agents including ipilimumab, combination therapy was characterized by high response rates and tolerable safety profile [Hellmann 2017]. The primary endpoint of the trial was safety with secondary endpoints of ORR and 24-week PFS. Exploratory endpoints included OS and efficacy by PD-L1 expression. In the trial, patients were randomly assigned (1:1:1) to receive nivolumab 1 mg/kg every 2 weeks plus ipilimumab 1 mg/kg every 6 weeks, nivolumab 3 mg/kg every 2 weeks plus ipilimumab 1 mg/kg every 12 weeks, or nivolumab 3 mg/kg every 2 weeks plus ipilimumab 1 mg/kg every 6 weeks until disease progression, unacceptable toxicities, or withdrawal of consent. The confirmed ORR was 47% (N3 q2w + I1 q12w) and 39% (N3 q2w + I1q6w). The median duration of response (DOR) was not reached. The rate of treatment-related adverse events in the Q12W (82%) and Q6W (72%) arms were comparable to monotherapy (72%). In the trial, Grade 3/4 adverse events were 37%, 33%, and 19% for the Q12W, Q6W and nivolumab monotherapy arms, respectively. Treatment-related Grade 3-4 AEs lead to discontinuation in 5% and 8% of patients in the Q12W and Q6W cohorts, respectively and were similar to nivolumab monotherapy. There were no treatment-related deaths. The treatment-related select AEs in patients administered the optimized dosing scheduled (3 mg/kg of nivolumab every two weeks plus 1 mg/kg of ipilimumab every six weeks) were skin related (36%), gastrointestinal (23%), endocrine (20%), and pulmonary (5%) and there were  $\leq$  5% treatment related grade 3/4 AEs per category.

The above data suggests combined CTLA-4 and PD-1 inhibition may drive deeper, more robust anti-tumor responses than single agent therapy. Supporting this in data from CM-142, a multi-cohort phase II trial of nivolumab with or without ipilimumab in advanced MSI-H CRC, presented at ASCO in 2017 demonstrated a 31% ORR for nivolumab alone compared to 55% for combination therapy with a median duration of response that was not reached for either arm [Andre 2017].

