8.2.5 Response

All patients will have their BEST RESPONSE from the start of study treatment until the end of treatment classified as outlined below:

**Complete Response (CR):** disappearance of *target* and *non-target* lesions and normalization of tumor markers. Pathological lymph nodes must have short axis measures  $< 10$  mm (Note: continue to record the measurement even if  $< 10$  mm and considered CR). Residual lesions (other than nodes  $< 10$  mm) thought to be non-malignant should be further investigated (by cytology specialized imaging or other techniques as appropriate for individual cases [Seymour 2017]) before CR can be accepted. Confirmation of response is only required in non-randomized studies.

**Partial Response (PR):** at least a 30% decrease in the sum of measures (longest diameter for tumor lesions and short axis measure for nodes) of target lesions, taking as reference the baseline sum of diameters. Non target lesions must be non-PD. Confirmation of response is only required in non-randomized studies.

**Stable Disease (SD):** Neither sufficient shrinkage to qualify for PR nor sufficient increase to qualify for PD taking as reference the smallest sum of diameters on study.

Progressive Disease (PD): at least a 20% increase in the sum of diameters of measured lesions taking as references the smallest sum of diameters recorded on study (including baseline) AND an absolute increase of  $\geq 5$  mm. Appearance of new lesions will also constitute progressive disease (including lesions in previously unassessed areas). In exceptional circumstances, unequivocal progression of non-target disease may be accepted as evidence of disease progression, where the overall tumor burden has increased sufficiently to merit discontinuation of treatment or where the tumor burden appears to have increased by at least 73% in volume. Modest increases in the size of one or more non-target lesions are NOT considered unequivocal progression. If the evidence of PD is equivocal (target or non-target), treatment may continue until the next assessment, but if confirmed, the earlier date must be used.

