Non-iUPD/PD	Non-iUPD/PD	Yes	iUPD	Remains iUPD unless iCPD confirmed based on - increase in size or number of new lesions previously identified

\* Using RECIST 1.1 principles. If no PSPD occurs, RECIST 1.1 and iRECIST categories for CR, PR and SD would be the same.

\*\* In any lesion category.

\*\*\* Previously identified in assessment immediately prior to this TP.

Table 3: iRECIST Best Overall Response (iBOR)

All patients will have their iBOR from the start of study treatment until the end of treatment classified as outlined below.

TPR1	TPR2	TPR3	TPR4	TPR5	iBOR
iCR	iCR, iPR, iUPD, NE	iCR, iPR, iUPD, NE	iUPD	iCPD	iCR
iUPD	iPR, iSD, NE	iCR	iCR, iPR, iSD, iUPD, NE	iCR, iPR, iSD, iUPD, iCPD, NE	iCR
iUPD	iPR	iPR, iSD, iUPD, NE	iPR, iSD, iUPD, NE, iCPD	iPR, iSD, iUPD, NE, iCPD	iPR
iUPD	iSD, NE	PR	iPR, iSD, iUPD, NE	iPR, iSD, iUPD, iCPD, NE	iPR
iUPD	iSD	iSD, iUPD, NE	iSD, iUPD, iCPD, NE	iSD, iUPD, ICPD, NE	iSD
iUPD	iCPD	Anything	Anything	Anything	iCPD
iUPD	iUPD	iCPD	Anything	Anything	iCPD
iUPD	NE	NE	NE	NE	iUPD

 
• Table assumes a randomized study where confirmation of CR or PR is not required.
 
• NE = not evaluable that cycle.
 
• Designation “T” for BOR can be used to indicate prior iUPD to aid in data interpretation.
 
• For patients with non-target disease only at baseline, only CR or non-CR/non-PD can be assigned at each TPR but is not shown in the table for ease of presentation.
 
					

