## 11.0 CENTRAL REVIEW PROCEDURES

11.1 Central Radiology Review

As part of the trial, copies of x-rays and/or scans may be collected to evaluate cancer response to treatment. There will be no central radiology review for this study.

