### 13.2 Endpoints and Analysis

The primary endpoint is ORR by RECIST 1.1 in immunotherapy naïve patients with advanced solid tumors with detectable mutations as determined by central blood-based assay (cfDNA for POLE/D1 mutations). Patients with detectable mutations in tissue but with no detectable mutations based on plasma cfDNA will be excluded from this analysis.

Response rates will be reported using percentages over all randomized patients with 90% exact confidence intervals (CI) of each arm in a non-comparative analysis. In addition, exact logistic regression models will be used to assess the effect of treatment on objective response probability, adjusting for mutational load values and trial site.

Secondary endpoints include: ORR of nivolumab monotherapy and of nivolumab combined with ipilimumab in all treated patients. Response rates will be reported using percentages over all patients who have received at least one dose of treatment with 90% exact CI of each arm in a non-comparative analysis. In addition, exact logistic regression models will be used to assess the effect of treatment on objective response probability, adjusting for mutational load values and trial site.

Duration of response (DOR) will be calculated from time of response to documentation of progression or death or censored at last time of disease assessment among all patients who have responded. Kaplan-Meier method will be used to estimate median duration of response and 90% confidence interval in each arm.

The responses assessed by iRECIST will be analyzed similarly as that by RECIST 1.1.

To assess the safety and characterize toxicities of nivolumab combined with ipilimumab and nivolumab monotherapy in all patients, estimation of the adverse event profile associated with treatment will be performed. All toxicities regardless of attribution will be reported using the CTCAE version 5.0 criteria. Adverse events rates will be reported using percentages with 90% exact CI.

Correlation between detectable mutations in tumor and detectable mutations in blood will be assessed by Fischer's exact test in each arm.

Detectable mutations in the initial study population are *POLE*/*POLD1* mutations based on plasma cfDNA.

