PFS and OS of nivolumab monotherapy and of nivolumab combined with ipilimumab in patients with advanced solid tumors with detectable mutations as determined by plasma cfDNA, and in all treated patients (detectable mutations in tissue or cfDNA) will be evaluated as exploratory endpoints.

Kaplan-Meier method will be used to estimate probabilities of OS and PFS for each arm. Patients alive at the time of trial analysis will be censored as of the date of their last disease assessment. Medians and 90% CI will be provided, if available. No formal comparisons will be made between the two arms. Adjusted analyses will be also consider mutational load as one of the covariates.

Tumors will undergo whole exome and RNA sequencing to evaluate the genetic landscape of mutated tumors in responders versus non-responders to immune checkpoint blockade.

Detectable mutations in the initial study population are *POLE*/*POLD1* mutations based on plasma cfDNA.

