### 13.3 Sample Size and Duration of Study

Approximately 100 immunotherapy-naïve patients with *POLE* or *POLD1* mutations identified at study entry via either circulating tumor DNA (cfDNA) central testing or prior local tumor assessment (to be confirmed retrospectively in such patients via central cfDNA testing) will be enrolled to this open-label, randomized, non-comparative trial.

We hypothesize that for this analysis treatment with immunotherapy will show a clinically relevant ORR of > 30% with single agent nivolumab or > 50% with combination nivolumab + ipilimumab in patients with advanced solid tumors with detectable *POLE* or *POLD1* mutations.

A sample size of 50 evaluable patients in each arm will achieve 90% power to show a clinically meaningful ORR. These calculations assume a single agent  $p_0 < 13\%$ ,  $p_1 > 30\%$  and combination therapy  $p_0 < 30\%$ ,  $p_1 > 50\%$ . Both assume a two-sided  $\alpha$  and  $\beta$  of 0.10.

Additional enrollment of up to 20% will be permitted as needed to replace patients found to not demonstrate *POLE* or *POLD1* mutations on central cfDNA.

As additional blood-based assays become available, the study may be amended to include additional cohorts.

Patients will be accrued from approximately four cancer treatment centers in the United States and four cancer treatment centers across Canada over a period of approximately 24 months.

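### Confirmation of CR and PR is waived because the study is randomized, but the primary ORR is a per-arm reading against a fixed rate, so randomization does not justify the waiver

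*Combined protocol and SAP*

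**What the plan says.** Section 8.2.5 ends its definitions of CR and of PR with the same sentence: "Confirmation of response is only required in non-randomized studies". The note under Table 3 in Section 8.3 carries this over to iRECIST: "Table assumes a randomized study where confirmation of CR or PR is not required". No other section asks for a second scan to confirm a response. The confirmatory scans in Sections 5.0, 8.3, 10.1 and 10.4 concern progression.

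The Treatment Schema and Sections 2.7.2, 13.1 and 13.3 call the trial non-comparative. Section 13.2 sets the primary reporting: "Response rates will be reported using percentages over all randomized patients with 90% exact confidence intervals (CI) of each arm in a non-comparative analysis". Section 13.3 sizes each arm on its own: "A sample size of 50 evaluable patients in each arm will achieve 90% power to show a clinically meaningful ORR". It gives p0 = 13% and p1 = 30% for nivolumab and p0 = 30% and p1 = 50% for the combination, with two-sided alpha and beta of 0.10. It does not say whether these rates count confirmed or unconfirmed responses, or where p0 comes from.

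The trial is open-label, and Section 11.1 states: "There will be no central radiology review for this study".

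**The concern.** The protocol itself accepts that a non-randomized study needs confirmed responses. Its exemption rests on the word randomized. That reasoning suits a trial in which a concurrent arm, read in the same way, gives the reference for the response rate. Here the reference in the primary analysis is a fixed number, and each arm is in effect a single-arm study: the setting in which the protocol's own sentence would require confirmation.

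Best response is taken over the whole treatment period. A shrinkage that meets the PR definition at one local reading, and is gone at the next scan, still makes the patient a responder. The arm's ORR is then set against a p0 that may have been defined on a stricter basis. What is at stake is whether an arm whose confirmed response rate is no better than p0 could be read as active.

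**Working it through.** **Inputs.** From Section 13.3: n = 50 per arm; p0/p1 = 0.13/0.30 and 0.30/0.50; two-sided alpha 0.10, so 0.05 in the upper tail; beta 0.10. From Section 13.2: exact 90% CI per arm. Two inputs are not in the documents: the success rule, inferred here as the lower limit of the exact 90% CI exceeding p0, and the share f of first responses that would fail confirmation, assumed to be 5%, 10% or 20%.

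**1. The plan's own figure.** Use a one-sample test with the arcsine approximation, h = 2·arcsin(√p1) − 2·arcsin(√p0) and power = Φ(h·√50 − 1.645).

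- Nivolumab: h = 0.4216, power = 0.909, required n = 49.
- Combination: h = 0.4115, power = 0.897, required n = 51.

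The stated 50 per arm and 90% power are reproduced as two separate one-sample tests. No comparison between arms enters the calculation.

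**2. Cut-offs under the inferred rule** (Clopper-Pearson lower 5% limit, n = 50).

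- Nivolumab: 11/50 gives 12.9%, 12/50 gives 14.5%. Success needs at least 12.
- Combination: 20/50 gives 28.3%, 21/50 gives 30.1%. Success needs at least 21.

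Exact error rates and power at these cut-offs:

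- P(X ≥ 12 | 0.13) = 2.4%, with power 0.861 at 0.30.
- P(X ≥ 21 | 0.30) = 4.8%, with power 0.899 at 0.50.

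**3. If p0 is a confirmed rate but unconfirmed responses are counted.** When the confirmed ORR equals p0, the ORR that is observed is p0/(1 − f). The false-positive rate is the binomial tail at that value.

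| f (assumed) | Nivolumab: observed ORR | P(X ≥ 12) | Combination: observed ORR | P(X ≥ 21) |
|---|---|---|---|---|
| 0 | 13.0% | 2.4% | 30.0% | 4.8% |
| 5% | 13.7% | 3.5% | 31.6% | 7.8% |
| 10% | 14.4% | 4.9% | 33.3% | 12.6% |
| 20% | 16.3% | 10.2% | 37.5% | 30.2% |

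The combination cut-off leaves almost no slack, so that arm passes 5% already at f = 5%. Nivolumab starts at 2.4% and passes 5% just above f = 10%.

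**4. If p0 is an unconfirmed rate.** Endpoint and p0 agree, and the first row of the table (2.4% and 4.8%) applies whatever f is.

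**5. What confirmation could cost in power.** If p1 is a confirmed rate, nothing changes. If p1 is an unconfirmed rate, the confirmed rate under the alternative is p1·(1 − f). At f = 10% these are 27% and 45%, so P(X ≥ 12 | 0.27) = 0.733 and P(X ≥ 21 | 0.45) = 0.714.

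**The case against.** The strongest reply is that the harm depends on a premise the documents leave open. A reader might infer that the false-positive risk of each arm is raised as the plan stands. Section 13.3 does not support that, because p0 could have been set on unconfirmed responses. This objection stands and limits the conclusion.

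A reader might also take the combination benchmark in Section 2.6 as proof of a mismatch: "The confirmed ORR was 47% (N3 q2w + I1 q12w) and 39% (N3 q2w + I1q6w". Those figures come from chemotherapy-naive NSCLC, and Section 13.3 does not use them. The rates nearest to p1 (31% and 55% in MSI-H colorectal cancer, Sections 2.3 and 2.6) are not labelled confirmed or unconfirmed. A mismatch is possible but not shown.

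The sentence "No formal comparisons will be made between the two arms" belongs to the PFS and OS text, so it should not carry the argument. Section 13.2 also plans an exact logistic regression for the effect of treatment on response. That model is additional, however, and the same section calls the primary ORR analysis non-comparative.

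There is no written success rule and no stated non-confirmation rate, so the size of the effect is conditional. A single 30% reduction is also not sufficient for PR: non-target lesions must not have progressed and no new lesion may appear. Duration of response, a secondary endpoint, would reveal short-lived responses. Finally, a concurrent arm would not reliably remove reader optimism in an open-label trial, and confirmation by the same local reader does not remove it either. Confirmation chiefly deals with transient shrinkage and chance measurement error.

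None of this restores the stated ground for the waiver, which is that the study is randomized.

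**Conclusion.** The point holds in a limited form and should be fixed. The waiver rests on randomization, but the primary ORR is a per-arm, locally read estimate sized against a fixed p0, so randomization does not justify it. It is also certain that unconfirmed ORR is at least as high as confirmed ORR, and that the basis of p0 and p1 is not stated.

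The inflation of the false-positive rate is conditional on three things: p0 being a confirmed rate, the inferred success rule, and the assumed share of 5% to 20%. Under those conditions it reaches 3.5% to 10.2% for nivolumab and 7.8% to 30.2% for the combination, against 5% allowed in the upper tail. If p0 is an unconfirmed rate there is no inflation. The direction is well supported; the size is illustrative.

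**What to change.** - **Section 8.2.5:** replace the waiver under CR and PR. For the primary ORR, a CR or PR counts only if it is confirmed by a repeat assessment at least 4 weeks later. The next scheduled 12-weekly scan suffices. It may fall after treatment ends if the response began on treatment; this must be said, because best response is currently counted only to the end of treatment.
- **Table 3 note (Section 8.3):** align it with the new wording.
- **Section 13.3:** state that p0 and p1 are confirmed rates, or restate them on that basis, with the power that follows.
- **Section 13.2:** report unconfirmed ORR as a sensitivity analysis.

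**Cost.** This is mainly wording. Patients in CR or PR are already scanned every 12 weeks for up to 2 years (Section 5.0, footnote 9) and every 3 months if they leave treatment with a response ongoing (Section 10.4). The reported ORR will be somewhat lower, because a response lost before the next scan no longer counts, and if the next scheduled scan is used it will be known about 12 weeks later. If p1 was an unconfirmed rate, power at n = 50 falls to about 0.73 and 0.71 at 10% non-confirmation, and the power statement would need to say so.

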**7.2 Duration of Therapy**

Patients should continue on trial treatment until RECIST 1.1/iRECIST defined progression or unacceptable toxicity or other treatment discontinuation criterion is met (see below).

An individual patient will not receive any further investigational product if any of the following occur in the patient in question:

- Patient request.

- Lost to follow-up.
- Patient is determined to have met one or more of the exclusion criterion for the trial.
- Participation at trial entry and continuing investigational therapy might constitute a safety risk.
- Pregnancy or intent to become pregnant.
- Initiation of alternative anti-cancer therapy including another investigational agent.

There is no maximum duration of treatment as patients may continue to receive investigational product beyond RECIST 1.1/iRECIST defined progression as long as they are continuing to show clinical benefit. In such cases, patients may continue to receive treatment following objective progression at Investigator's discretion and as agreed with the patient.

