Patients that are clinically well may continue on therapy following RECIST progression with new lesions or increase in target lesions if the increase in disease burden does not meet the definition of PD by immune response criteria [Seymour 2017]. In this situation, patients do not have unequivocal progression until immune response criteria are met (see Table 1 below).

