### 8.3 Immune-Related Response Assessment

Overall response will also be assessed using iRECIST [Seymour 2017]. Immunotherapeutics may result in infiltration of immune cells leading to transient increase in the size in malignant lesions, or undetectable lesions becoming detectable. The criteria are identical to those of RECIST 1.1 in many respects but have been adapted to account for instances where an increase in tumor burden, or the appearance of new lesions, does not reflect true tumor progression.

Key differences are described below. All responses defined using iRECIST criteria are designated with a prefix. iRECIST time-point and best overall responses will be recorded separately.

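### RECIST 1.1 best response is not closed at RECIST 1.1 progression, so a response reached after PD literally qualifies for the primary ORR

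*Combined protocol and SAP*

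**What the plan says.** Section 13.2 names the endpoint: "The primary endpoint is ORR by RECIST 1.1 in immunotherapy naïve patients with advanced solid tumors with detectable mutations". It gives no rule on when a response must occur relative to progression.

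Section 8.2.5 sets the window: "All patients will have their BEST RESPONSE from the start of study treatment until the end of treatment classified as outlined below". PR needs a fall of at least 30%, "taking as reference the baseline sum of diameters". PD needs a rise of at least 20% and 5 mm from the smallest sum on study, or a new lesion. If PD is equivocal, treatment may go on to the next assessment, and the earlier date is used if PD is then confirmed.

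Treatment may outlast progression. Section 7.2 says "patients may continue to receive investigational product beyond RECIST 1.1/iRECIST defined progression as long as they are continuing to show clinical benefit", and section 10.1 keeps clinically stable patients with iUPD on treatment until the next assessment. Section 8.2.5 has a paragraph on clinically well patients who continue after RECIST progression without meeting the immune criteria for PD. It ends: "In this situation, patients do not have unequivocal progression until immune response criteria are met (see Table 1 below". Table 1 is the RECIST 1.1 table.

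For the immune criteria, section 8.3 states that "iRECIST time-point and best overall responses will be recorded separately". Table 3 uses the same window: "All patients will have their iBOR from the start of study treatment until the end of treatment classified as outlined below".

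**The concern.** The RECIST 1.1 window ends with treatment, treatment can continue after PD, and PR is judged against baseline. A scan after PD can therefore fall inside the window and meet the PR definition. Table 1 classifies one time point at a time and carries no earlier PD forward. The closing sentence of the continuation paragraph sits in the RECIST section and cites the RECIST table, so it invites a reader to treat RECIST PD as provisional.

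The primary ORR is at stake: it could absorb late responses that the separate iRECIST endpoint exists to record. Duration of response (sections 8.4 and 13.2) could begin after a documented PD, making one patient a progression event and then a responder under the same criterion. Section 11.1 provides no central radiology review, so investigators in an open-label trial would settle the question, possibly differently from site to site.

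**Working it through.** **Does a post-PD response qualify as written?** Take an illustrative patient with no new lesions, non-target disease not progressing, and a target sum of 100 mm at baseline.

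- First assessment 120 mm: up 20% and 20 mm, so RECIST 1.1 PD and iUPD.
- Clinically stable, stays on treatment, and is rescanned 4 to 8 weeks later (section 8.3).
- Rescan 70 mm: down 30% from baseline. Table 1 gives PR (target PR, non-target non-PD, no new lesion); Table 2 gives iPR.
- Both scans precede the end of treatment, so the section 8.2.5 window contains the PR.

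Under iRECIST this is expressly allowed: section 8.3 says that prior iUPD does not bar a later iPR. For RECIST 1.1 no sentence allows or bars it.

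**The plan's own figure.** Section 13.3: 50 evaluable per arm, 90% power, two-sided alpha 0.10 (0.05 per tail); p0 = 13%, p1 = 30% for nivolumab; p0 = 30%, p1 = 50% for the combination.

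n = [(z0.95·√(p0(1−p0)) + z0.90·√(p1(1−p1))) / (p1−p0)]²

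- Nivolumab: [(1.645×0.3363 + 1.282×0.4583)/0.17]² = 45.004, so 46.
- Combination: [(1.645×0.4583 + 1.282×0.5)/0.20]² = 48.6, so 49.

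The larger arm gives about 50, so the stated size reproduces. Power at n = 50 is 92.2% and 90.7% by this approximation, and 86.1% and 89.9% by the exact binomial with the thresholds below.

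**Threshold (assumed).** The documents state no success rule. I assume success means that the lower limit of the 90% exact interval in section 13.2 exceeds p0, with 50 patients as denominator.

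- Nivolumab: 11/50 has lower limit 12.9% (fails); 12/50 has 14.5% (passes).
- Combination: 20/50 has 28.3% (fails); 21/50 has 30.1% (passes).

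One patient is 1/50 = 2 points, so one reclassified patient can change an arm's result.

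**Effect at p0.** Let d be the share of patients whose only response comes after RECIST 1.1 PD. The documents give no value; 0 to 6 points is assumed. If the pre-PD rate is p0 and these patients count, the chance of success is P(X ≥ r), X ~ Binomial(50, p0 + d).

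| d (points) | Nivolumab, r = 12 | Combination, r = 21 |
|---|---|---|
| 0 | 2.4% (p = 0.13) | 4.8% (p = 0.30) |
| 2 | 6.3% (p = 0.15) | 8.8% (p = 0.32) |
| 4 | 13.1% (p = 0.17) | 14.8% (p = 0.34) |
| 6 | 23.0% (p = 0.19) | 22.9% (p = 0.36) |

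**The other direction.** If p1 was meant to include such responses and they are excluded, power is P(X ≥ r) at p1 − d. For d = 2 and 4 points it falls from 86.1% to 78.2% and 67.8% (nivolumab), and from 89.9% to 83.9% and 76.0% (combination).

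**The case against.** The strongest reply is that the intent is clear. Section 8.3 presents iRECIST as the adaptation for growth or new lesions that are not true progression. It reserves confirmation of PD, and response after unconfirmed PD, for iRECIST, and it records iRECIST best response separately. The Table 2 footnote says that the two criteria agree on CR, PR and SD when there is no pseudoprogression, which implies that they differ when there is. The continuation paragraph in 8.2.5 is mainly about who may stay on therapy and still calls the event RECIST progression. RECIST 1.1 is also adopted by reference, and the guideline may supply the sequencing rule; that cannot be checked from these documents.

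All of this stands as evidence of intent. It does not supply the missing rule, because the window that 8.2.5 does state runs to the end of treatment.

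The reply does defeat several stronger readings that a reader might infer:

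- That the plan declares post-PD shrinkage to count. It never says so; the literal window merely admits it.
- That RECIST 1.1 is written more loosely than iRECIST because Table 3 fixes iCPD and Table 1 has no such lock. Table 1 is a time-point table, whose counterpart is Table 2; Table 3 is a best-response table.
- That the two endpoints have become one measure. Section 8.3 and the Table 2 footnote point the other way.
- That ORR is shown to be biased upward against a RECIST 1.1 benchmark. Section 13.3 names no criterion or source for p0.
- That shrinkage after confirmed progression would routinely enter. Section 10.2 takes patients off study at unequivocal progression, although section 7.2 allows treatment beyond progression.

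A new lesion that is still present keeps the time point at PD under Table 1, so the clearest case is target-lesion PD followed by shrinkage.

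**Conclusion.** The point holds as a defect in the endpoint definition. The protocol states a RECIST 1.1 best-response window that is not cut at RECIST 1.1 PD, and a later CR or PR satisfies it as written, against the apparent intent of section 8.3. The closing sentence of the continuation paragraph adds to the ambiguity but is not its only source.

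The size is conditional. Two points of ORR per patient is arithmetic at n = 50. The changes in the chance of success rest on an assumed success rule, an assumed 2 to 6 points of post-PD response, and a true pre-PD rate equal to p0. They show how sensitive the thresholds are; they do not forecast an inflation. The sample size is not in error. Because the primary endpoint depends on it, the rule should be settled before responses are analysed.

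**What to change.** In sections 8.2.5 and 13.2, state:

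1. RECIST 1.1 best response is the best category recorded from start of treatment up to the first RECIST 1.1 PD or end of treatment, whichever comes first. Responses after that PD count only toward iRECIST.
2. PD judged equivocal under section 8.2.5 closes the window only if it is confirmed at the next assessment, and then from the earlier date. If it is not confirmed, the window stays open and no PD is recorded. Without this clause, a patient with equivocal, never-confirmed PD could lose later responses while having no progression date.
3. The sentence on unequivocal progression in the continuation paragraph does not change the RECIST 1.1 category or date.

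This concerns classification only and leaves the treatment rules untouched. The cost is a few sentences and matching case report form guidance. No new data are needed, since iRECIST responses are already recorded separately, and n is unchanged. The downside is that the RECIST 1.1 ORR may be slightly lower. The sponsor should also confirm that p0 and p1 were set on the same basis, given the power loss shown above if p1 included late responses.
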